3.2. Inclusion and Exclusion Criteria

3.2.1. Inclusion Criteria

- Age \geq 21 years on date of consent
- Optimal pharmacologic therapy is defined by published guidelines from the American Heart Association and the American College of Cardiology
- Existing indication for CRT device with initial implant scheduled within 1 calendar month on or from date of randomization
- Ischemic or nonischemic cardiomyopathy
- LVEF \leq 35% within 12 calendar months prior to or on consent date by angiographic, radionuclide, or echocardiographic methods
- NYHA class II-IV (ambulatory) on consent date
- QRS \geq 120 ms for LBBB and \geq 150 ms for non-LBBB patients within 1 calendar year prior to or on consent date
- Continuous AF $>$ 3 calendar months when no further efforts to restore sinus rhythm are feasible or pursued**

***ECG evidence of AF will be required at enrollment and at 2 additional time points, one within 3 calendar months and one \geq 3 calendar months prior to enrollment, with no intervening ECGs revealing sinus rhythm and/or no successful effort to restore sinus rhythm for $>$ 24 hours*

OR

- Active CRT-D device implanted within the last calendar year with $<$ 15% improvement in LVSEV from pre-implant cardiac imaging. The evaluation of LVSEV post implant must be within the last three calendar months.
- Continuous AF $>$ 3 calendar months when no further efforts to restore sinus rhythm are feasible or pursued (see definition above)

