5. METHODS AND STUDY PROCEDURES

5.1. Study Procedures

This study is designed as a 2-arm unblinded randomized clinical trial. A total of 40 subjects receiving or with CRT-D devices for standard clinical indications will be randomized 1:1 to the atrioventricular junctional (AVJ) ablation or to a control arm without ablation, stratified by enrolling site. All subjects will be followed for 6 months. The study procedures to be conducted for each subject enrolled in the study are presented in tabular form (Schedule of Activities) below and described in the text that follows:

Table 1. Schedule of Activities

PROCEDURES	Screening Visit	Randomization - Baseline – Procedure Visits		Follow-up Visits		
	Visit 1	Visit 2	Visit 3	Visit 4	Visit 5	Visit 6
	Consent within 1 calendar month prior to randomization	Day 1	Within 1 calendar month after randomization date	1 calendar month \pm 7 days	3 calendar months \pm 14 days	6 calendar months \pm 14 days
	Screening	Randomization-Baseline	Ablation \pm CRT-D	1 month post randomization	3 months post randomization	6 months post randomization
Informed Consent	✓					
Pregnancy test when applicable (within 7 days prior to randomization date)	✓					
Eligibility Confirmation	✓					
Randomization		✓				
Demographics /Medical History		✓				
Physical Exam (Limited)		✓		✓	✓	✓
CV Medication Prescribed		✓			✓	✓
Symptom Assessment		✓		✓	✓	✓
Quality of Life		✓**				✓
12-lead ECG		✓*		✓*	✓*	✓*
Echocardiogram		✓*				✓
CRT-D Implantation†			✓*			
CRT-D Programming /Episode Reports			✓*	✓*	✓*	✓*
AVJ ablation			✓*			
Adverse Event			✓	✓	✓	✓
Heart Failure Event				✓	✓	✓
Protocol Deviations		✓	✓	✓	✓	✓
Subject Status			✓	✓	✓	✓

* standard of care procedures

** obtain quality of life questionnaire prior to informing subject of treatment assignment

† Ablation only for active CRT-D devices

CRT-D Implantation and Programming: For subjects having an index device procedure, the CRT-D will be implanted following clinically approved indications using standard techniques and leads will be placed in the right ventricle (RV) and the coronary sinus for biventricular (BiV) pacing. In case left ventricular (LV) lead cannot be positioned in the coronary sinus, direct epicardial techniques are permitted

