Randomization as a method of experimental control has been extensively used in human clinical trials. It prevents the selection bias and insures against accidental bias. It produces the comparable groups and eliminates the source of imbalance after treatment assignment. Finally, it permits the use of probability theory to express the likelihood of chance as a source for the difference of the final outcome. Randomization in this study will occur at visit 2. It should be noted that that visit 2 could take place on the same day as visit 1 and visit 3.

1. CRT-D device implantation or
2. CRT-D device implantation and AVJ ablation procedure

For subjects with an existing CRT-D device

1. Ablation
2. Medical management

Subjects will be notified that randomization is part of this study during the consent process. Subject will be informed which randomized arm they have received after completing the quality of life questionnaire. Subject will be notified that either treatment arm may be less or more effective, or may have more or less side effects.

Randomization will be stratified by enrolling site and generated per the scheme described in Section 11. The randomization strings for treatment assignment will be provided to the database programmer at the coordination site by chief statistician [name] and uploaded in the electronic data capture system with appropriate testing and validation that the system is working correctly prior to the beginning of subject

randomization. The enrolling site has full responsibility for completion of the CRFs required for subject randomization. The enrolling site may contact the data center project manager and will notify about randomization results only if the enrolling site has no internet access or the web base program will automatically assign the randomization treatment assignment and subject ID based on the randomization strings provided by the biostatistician. The randomization result is viewed by the enrolling site in the eDC system following randomization or documented on the paper CRF which is returned to the enrolling site if randomization cannot be done through the eDC system. All eligibility criteria will be confirmed prior to providing the randomization treatment assignment/subject ID to the enrolling site.

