CRT-D implantation (unless subject has an existing, active CRT-D device) and AVJ ablation (in subjects randomized to AVJ ablation arm) are expected to be performed during this visit which must occur within on or within 1 calendar month after randomization date. These procedures could be performed on the same day as Baseline Visit 1 that will reflect usual clinical practice. Both procedures usually are performed on the same day while the subject is in electrophysiology lab for CRT-D implantation. However, the timing of the AVJ ablation is left to the discretion of physician. It is recommended that AVJ ablation be performed within 2 days of CRT-D implantation. Programming of CRT-D should need to be adjusted at the time of AVJ ablation as described above.

5.6. **Visit 4: Follow-up at 1 calendar month after Randomization** (1 calendar month \pm 7 days)

During this follow-up visit investigators/coordinators should:

- Perform limited clinical assessment, collect vital signs Obtain a copy of standard 12-lead ECG
- Assess CRT-D implant status
- Perform CRT-D interrogation and reprogramming as needed
- Obtain information regarding adverse events and congestive heart failure

5.7. **Visit 5: Follow-up at 3 calendar months after Randomization** (3 calendar months \pm 14 days)

During this follow-up visit investigators/coordinators should:

- Perform limited clinical assessment, collect vital signs and collect data on current prescribed CV medications
- Obtain a copy of standard 12-lead ECG
- Perform CRT-D interrogation and reprogramming as needed
- Obtain information regarding adverse events and congestive heart

5.8. **Visit 6: Follow-up at calendar 6 months after Randomization** (6 calendar months \pm 14 days)

During this follow-up visit investigators/coordinators should:

- Perform limited clinical assessment, collect vital signs and collect data on current prescribed CV medications
- Obtain a copy of standard 12-lead ECG
- Perform Echocardiogram per study echo acquisition manual
- Perform CRT-D interrogation and reprogramming as needed
- Obtain information regarding adverse events and congestive heart
- Quality of Life assessment
- Document closeout of subject participation in the study

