8. RISK/BENEFIT ASSESSMENT

8.1. Potential Risks

Early risk to patients: The ablation catheter needs to be introduced through the femoral veins. This can result in either bleeding (hematoma) or thrombosis. The former was reported in 1 of 252 subjects (0.4%) in one study; the latter was reported in 1 of 156 subjects (0.6%) in another study. When the ablation is performed after implantation of the CRT device, it is possible to dislodge one of the implanted leads with the ablation catheter;

this was observed in 2 of 156 subjects (1.2%) in a prior study. This complication would require repositioning of the lead(s) that dislodged.

Late complications: There are 2 feared late complications of AV junction ablation. The first is that dislodgement of the ventricular lead in a pacemaker dependent subject could be fatal. However, a stable underlying escape rhythm is present in 67% of subjects following ablation. In addition, each subject in this trial will be undergoing biventricular pacing. It would be distinctly unusual for both the right and left ventricular leads to dislodge at the same time. Dislodgement of one ventricular lead would lead to loss of biventricular pacing but would still allow the other ventricular lead to pace the heart. In addition, contemporary left ventricular leads are multipolar, providing additional pacing redundancy.

The second feared complication is polymorphic ventricular tachycardia. In early trials of AV junction ablation, sudden cardiac death was observed in ~5% of patients. It was subsequently recognized that this was due to bradycardia-dependent polymorphic tachycardia. This adverse event can be eliminated by gradually reducing the lower pacing rate after initial programming is set at a higher than usual lower rate cutoff (as has been designed in this trial). Arrhythmic mortality was observed in only 2 of 252 subjects (0.8%) when such a protocol was routinely employed in a post-AV junction trial of pacemaker patients. In our study, all subjects will have an implantable defibrillator; thus, in the extremely rare event that a subject develops post-ablation polymorphic ventricular tachycardia, the defibrillator would be able to resuscitate the subject.

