11. STATISTICAL METHODS AND POWER CONSIDERATIONS

Overall Study Design and Primary Endpoint: This study is designed as a 2-arm unblinded randomized clinical trial. A total of 40 subjects receiving CRT-D will be randomized 1:1 to AVJ ablation or control arm (without AVJ ablation), stratified by enrolling site. The primary endpoint is the binary response defined as $\geq 15\%$ reduction in LVESV from baseline to 6 months.

Randomization Scheme: Enrolled subjects will be 1:1 randomized to AVJ ablation (with CRT-D) or control (CRT-D only). The randomization sequence will consist of a string of random 4- and 6-blocks. That is, there will be a 50% chance that the first block will consist of 4 subjects (2 AVJ ablation + 2 control, in random order), and a 50% chance that it will contain 6 subjects (3 AVJ ablation + 3 control, in random order). Each subsequent block will similarly be of random size. This procedure makes it very difficult for anyone to predict whether the next treatment assignment will be AVJ ablation (or control), helping to ensure integrity of the study. In contrast, if each block were of size 4, then it would be trivial to perfectly predict every 4th treatment assignment as well as the 3rd, if the first two were both AVJ ablation or both control, which would be undesirable. Randomization will be stratified by enrolling site. The randomization scheme will be generated by chief statistician [name] and provided to the CDC per Section 5.

Endpoint: The primary endpoint is the binary response defined as $\geq 15\%$ reduction in LVESV from baseline to 6 months.

Power and Sample Size: Randomizing 20 subjects per arm (for a total of 40 subjects), and allowing for up to 10% drop-out due to withdrawal, death, or inadequate imaging, we expect at least $n=18$ evaluable subjects per arm. This sample size will provide 80% power to detect an absolute change of 50% in response rates, using a 0.05 level 2-sided Fisher exact test, assuming the actual response rate in the AVJ ablation arm is 80-85%, as in

Gasparini 2006 (1) and Ferreira 2008 (6), where the empirical change in response rates was $\Delta = 49\%$ and 33% , respectively.

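### New-implant subjects are randomized before the CRT-D is implanted, so the arm can be known while leads are placed and failed implants stay in the ITT comparison

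*Combined protocol and SAP*

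**What the plan says.** The protocol has two entry routes (Section 3.2.1). One is for patients awaiting a first device, with "Existing indication for CRT device with initial implant scheduled within 1 calendar month on or from date of randomization". The other is for patients who already have an active CRT-D and have not remodelled. The share of the 40 expected from each route is not stated.

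- **Order.** Section 5.1: "Randomization in this study will occur at visit 2". Table 1 and Section 5.5 put implant and ablation at Visit 3, "which must occur within on or within 1 calendar month after randomization date". Section 5.1 adds that "visit 2 could take place on the same day as visit 1 and visit 3". This shortens the gap but leaves the order unchanged.
- **Who knows the arm.** Section 2.1 describes the trial as unblinded. Under Section 5.1 the site reads the result in the EDC system once the subject is randomized. No step withholds it from the implanter.
- **Difficult LV leads.** Section 5.1: "In case left ventricular (LV) lead cannot be positioned in the coronary sinus, direct epicardial techniques are permitted". This is a permission, and nothing says how a subject is handled if no working LV lead results.
- **Analysis.** Section 11 specifies an ITT Fisher exact test on response. Section 5.1 keeps failed ablations in their assigned arm. Failed implants are not mentioned.
- **Allowance.** Section 11 takes 20 per arm to 18 evaluable by "allowing for up to 10% drop-out due to withdrawal, death, or inadequate imaging".

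**The concern.** Ablation is the only intended difference between the arms, so the question is what ablation adds to CRT. On the new-implant route, the step that delivers CRT comes after the arm is known. Two things follow.

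First, an operator who knows that a patient is about to become pacemaker dependent could persist differently with lead placement. The blinded echo core lab protects the reading of LVESV; it does not protect the implant. That the implanter knows the arm is an inference, but a strong one: the trial is open, the site sees the result, implant and ablation usually share a session (Section 5.5), and no concealment is described.

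Second, a subject whose implant does not yield biventricular pacing is already randomized. If a 6-month echo is obtained, that subject enters the primary comparison although the effect of ablation on top of CRT cannot show itself there.

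The second costs power in a trial with little to spare. The first could bias the contrast, but only if placement really differed by arm.

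**Working it through.** **Inputs.** From Section 11: 20 randomized and 18 evaluable per arm; two-sided Fisher exact test at 0.05; ablation-arm response 80-85%; difference 50 points, so control response 30-35%. Not in the documents, and therefore assumed: the failure rate *f* among new implants (2%, 5%, 10%), no response after a failure, and the share *w* of subjects who are new implants (all, or half).

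**1. The plan's own figure.** 20 × (1 − 0.10) = 18. Power is the sum of the two binomial probabilities over all tables (x₁, x₂) with Fisher p ≤ 0.05. At 18 per arm:

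- 0.80 v 0.30: 83.5%
- 0.85 v 0.35: 84.2%

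At 17 per arm the values are 79.2% and 80.1%, so 18 is the smallest size that reaches 80% across the stated range. The plan's figure reproduces, with a margin of 3.5 to 4.2 points.

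**2. Equal failure in both arms.** With g = w × f, each response rate becomes (1 − g) × p and the difference becomes (1 − g) × 50 points. For example, at w = 1 and f = 5%: 0.95 × 0.80 = 0.760, 0.95 × 0.30 = 0.285, difference 47.5 points, power 78.5%.

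| Failure rate among new implants | All new implants | Half new implants |
|---|---|---|
| 0% | 83.5-84.2% | 83.5-84.2% |
| 2% | 81.6-82.1% | 82.5-83.2% |
| 5% | 78.5-78.9% | 81.1-81.6% |
| 10% | 73.1-73.2% | 78.5-78.9% |

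If failures respond at 10% instead of never, the all-new-implant figures barely move (78.5-78.9% at 5% failure). In subjects, 5% of 40 is 2 and 10% of 40 is 4.

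**3. Failure that differs by arm, with no ablation effect.** Take 0% failure in one arm and 10% in the other:

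- Base rate 30%: 0.300 − 0.270 = 3.0 points; rejection rate 2.4%
- Base rate 35%: 0.350 − 0.315 = 3.5 points; rejection rate 2.6%

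With no difference at all, the rejection rates are 2.2% and 2.4%. All lie below the nominal 5%, because Fisher's test is conservative at this size.

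**4. After the change.** If only subjects with confirmed biventricular pacing are randomized and 18 per arm remain evaluable, power stays at 83.5-84.2%.

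**The case against.** The case for leaving the order alone has real substance.

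- **ITT retention is valid.** Randomizing before a combined procedure tests the strategy as offered. Randomizing afterwards tests ablation given a successful implant. Choosing between them is a choice of estimand. This stands, although Sections 1 and 11 frame the question as what ablation adds to CRT.
- **The power loss rests on assumptions.** No failure rate is given, the epicardial option reduces final failures, and existing-device subjects are not exposed. A reader might infer that 5% failure puts the trial below its stated 80%. That needs all 40 to be new implants; if half are, power is still above 81%. Section 11 also says its response rates are ITT rates. That sentence concerns crossovers, but if it is read broadly, part of the dilution may already be counted.
- **Some losses are already allowed for.** A subject whose implant is cancelled may withdraw or have no usable echo, both of which fall within the 10%. Only failures with an evaluable echo add to it.
- **Safeguards exist.** These include standard implant technique, similar programming in both arms, LV-lead status and pacing percentage at each follow-up, and blinded reading.

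Two stronger readings are tempting and are not supported. A reader might infer a materially inflated false-positive rate: a 10-point shift in one arm would raise rejection to 5.2-5.5%, and a 15-point shift to 9.4-9.7%. Nothing in the documents supports shifts of that size. Through failed leads alone, 10 points would need a between-arm difference in failure of about 22-25% (0.10/0.45 to 0.10/0.40), and 15 points about 30-33% (0.15/0.50 to 0.15/0.45). Even the 10-point shift only brings the test to about its nominal level.

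A reader might also infer that the order undermines the safety reasoning in Section 8.1, "In addition, each subject in this trial will be undergoing biventricular pacing". It does not. Ablation accompanies or follows the implant whenever the assignment is drawn.

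**Conclusion.** The point holds as a cheap design improvement and does not expose an error in any stated figure. The order of events is explicit; the implanter's knowledge of the arm is a well-supported inference. Failed implants with a 6-month echo remain in the primary comparison because the analysis is ITT and no rule says otherwise.

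The supportable cost is dilution. Each 5% of randomized subjects without working biventricular pacing takes 2.5 points off the 50-point difference and about 5 points off power, against a margin of 3.5 to 4.2 points. This rests on an assumed failure rate, no (or little) response after failure, equal failure in both arms, and an unstated mix of the two routes. Bias is possible in principle but is not shown. At the extreme of the assumed range it is 3.0 to 3.5 points, small beside the 50-point target.

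**What to change.** For new implants, keep consent, eligibility, baseline echo and KCCQ before the implant. Draw the EDC assignment only once the implant is complete and biventricular pacing is confirmed, in the same session or within the implant-to-ablation interval that Section 5.1 already allows. Subjects without working biventricular pacing are then not randomized and do not count toward the 40. The existing-device route already works this way.

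Amend Table 1 and Sections 5.1, 5.4 and 5.5. Reword the window in Section 3.2.1 ("initial implant scheduled within 1 calendar month on or from date of randomization") so that it runs from a date before the implant, such as consent. Adverse event reporting in Sections 7.3 and 7.4 starts at randomization, so it would need an earlier start for this route if implant complications are still to be captured.

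If the sponsor prefers to keep the draw at Visit 2, the minimum is to withhold the result from the site until the leads are placed. This removes the implanter's knowledge but leaves failed implants in the ITT set, so Section 11 should say how they are analysed. Under either option, report LV-lead success by arm.

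The cost is modest: sites randomize from the EP lab, hold ablation slots for some subjects later assigned to control, and have a few consented subjects who are never randomized. The result then applies to patients with a successful CRT implant. Knowledge of the arm during follow-up is unaffected.

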5.2. Subject Consent

Each potential subject will have the protocol described to them by one of the physicians or research coordinators at the enrolling sites. Potential subjects will sit down with the coordinator or physician and have the opportunity to ask questions. Those who meet inclusion/exclusion criteria will then be asked to sign consent for study participation. At this time they will sign an "informed consent" form that is fully approved by the local IRB following local IRB consent administration regulations. It is the responsibility of the investigator to ensure that subjects are eligible to participate in the study prior to enrollment and throughout the study. Once informed consent has been obtained, all screening tests and procedures have been assessed and study eligibility has been confirmed, subjects will be randomized and assigned a unique subject identification number. The enrolling site will enter data in the web base system and the system will assign the subject ID after study eligibility criteria are met. The scheme for assigning subject ID is as follow: first 2 numbers are assigned for enrolling site and will not change for duration of the study. Next two numbers are specific to a randomized subject in the enrolling site.

The principal investigator ensures that informed consent from each potential research participant will be obtained by an IRB approved consent designee and documented. The following person may obtain consent: the principal investigator, sub-investigators, or study team members listed on the IRB application form as a consent designee. Each individual who will interact with potential research participants to obtain consent will submit evidence of human subject compliance training per local IRB regulations.

5.3. Visit 1: Screening

- Potential subjects will be screened to determine eligibility for participation in the study per medical record review. Potential subjects will be identified based on planned CRT-D implant or existing active CRT-D device. Those who fulfill the study eligibility criteria and current indication for CRT-D implantation or existing active CRT-D device can be approached for informed consent, but additionally ECG evidence of AF will be required at consent and meet study criteria prior to patient randomization. The screening visit might occur on the same day as the Baseline and procedure visit described below.

